9.3 Drug Inventory

The Sponsor will supply sufficient quantities of the study formulation for the following: (1) completion of this study and (2) retention, as per applicable regulations. All drug supplies provided for this study will be stored in a secure area with restricted access, under controlled storage conditions described in the product package labelling, unless otherwise instructed per protocol.

Records will be made of receipt and dispensing of nifedipine, omeprazole/sodium bicarbonate, and SmartPill™ supplied. It is the responsibility of the Sponsor to

ensure that all drug supplies provided for the study are manufactured under current Good Manufacturing Practices (cGMP) and are suitable for human use.

9.4 Disposition of Unused Study Drug (Nifedipine, omeprazole/sodium bicarbonate, SmartPill™)

Upon completion or termination of the study, all remaining study supplies will be retained according to applicable regulations. Once the retention period has elapsed, any remaining unused drug will be returned to the Sponsor in the original containers, or destroyed, as directed in writing by the Sponsor.

10.0 Potential Risks and Benefits

10.1 Potential Risks

Nifedipine

The controlled and open trials with chronic dosing of nifedipine extended-release tablets in hypertension and angina patients were included in the evaluation of adverse experiences. It is noteworthy that these potential risks derived from clinical studies with chronic multiple-dose administration of nifedipine in subjects with cardiovascular (e.g. hypertension and angina) diseases.

- The most common side effect reported with PROCARDIA XL was edema which was dose related and ranged in frequency from approximately 10% to about 30% at the highest dose studied (180 mg).
- Other common adverse experiences reported in patients in a placebo-controlled trials include, headache (15.8%), fatigue (5.9%), dizziness (4.1%), constipation (3.3%), and nausea (3.3%).
- Other adverse reactions were reported sporadically with an incidence of 1.0% or less.
- Gastrointestinal obstruction resulting in hospitalization and surgery, including the need for bezoar removal, has occurred in association with nifedipine extended-release tablets, even in patients with no prior history of gastrointestinal disease.
- Cases of tablet adherence to the gastrointestinal wall with ulceration have been reported, some requiring hospitalization and intervention.

Other serious side effects reported with PROCARDIA XL (nifedipine) use were:

- **Myocardial infarction [heart attack] (4%)**
- Pulmonary edema [fluid accumulation in the lungs] (2%)
- Ventricular arrhythmias [abnormal heartbeat] or conduction disturbances (0.5%)

Omeprazole/sodium bicarbonate

Each capsule contains omeprazole and sodium bicarbonate. Subjects will be asked to consult the Investigator if on a sodium restricted diet or have Bartter's Syndrome (a rare kidney disorder) or at risk of developing congestive heart failure (CHF).

- Omeprazole/sodium bicarbonate may increase risk of getting severe diarrhea caused by an infection (*Clostridium difficile*) in intestines.
- Multiple daily doses of proton pump inhibitor medicines for a long period of time (a year or longer) may
 - Have an increased risk of fractures of the hip, wrist or spine.
 - Increase the risk of inflammation to your stomach lining.
- Possibility of vitamin B-12 deficiency if you have been on omeprazole/sodium bicarbonate for a long time (more than 3 years).
- Low magnesium can happen in some people who take a proton pump inhibitor medicine for at least 3 months.
- The most common side effect reported in patients include, headache, abdominal pain, nausea, vomiting and gas.
- Additional adverse reactions that could be caused by sodium bicarbonate include metabolic alkalosis, seizures, and tetany.
- Other adverse reactions were reported sporadically with an incidence of 1.0% or less.

A long term use of omeprazole/sodium bicarbonate may cause serious side effects including chronic inflammation of the stomach lining (Atrophic Gastritis).

SmartPill™

The risk involved for subjects with the SmartPill™ Capsule Motility procedure is non-passage of the capsule through the intestinal tract. If there is delay in passage of the capsule, and the capsule is located in the stomach, a pro-motility drug could be administered to assist in emptying the capsule from the stomach. Alternatively, endoscopy could be performed in order to retrieve the capsule. If located in the colon, laxative therapy could be administered to facilitate capsule movement, or a colonoscopy could be performed in order to retrieve the capsule. This can occur when a subject has a blockage. Subjects must inform study staff or study doctor in such instance.

Subjects must avoid MRI machines during the SmartPill™ Capsule Motility procedure until 7 days after the study.

10.2 Potential Benefits

While it may not provide direct benefit to subjects, the importance of the knowledge that may result from the study may enhance regulatory review on oral modified-release drug products in which the controlled release rate of drug delivery into the gastrointestinal lumen is a function of gastric pH.

11.0 SAFETY ASSESSMENT

BioPharma Services USA Inc. has established SOPs in conformity with regulatory requirements to ensure the timely, accurate and complete reporting of safety information.

PI/Sub-Investigators at BPSUSA are responsible for monitoring the safety and for providing appropriate medical care for subjects who have entered this trial (i.e., from the signing of ICF onwards). In addition, the PI/Sub-Investigator remains responsible for following-up all AEs.

Each subject will be carefully questioned and/or examined by the PI/Sub-Investigator or a medically qualified delegate (i.e., authorized by the Investigator, in a separate form, to record AEs) to obtain information regarding AEs. All AEs will be reported and documented as stated below

11.1 Definitions

Adverse Event (AE) – is any untoward medical occurrence in clinical trial subject who are administered with any of study drugs (nifedipine, omeprazole/sodium bicarbonate and SmartPill™) and which does not necessarily have a causal relationship with this treatment. An adverse event can therefore be any unfavorable and unintended sign (e.g. an abnormal laboratory finding), symptom, or disease temporally associated with the use of a study drug, whether or not considered related to the study drug.

Adverse Drug Reaction (ADR) of study drug any of study drugs (nifedipine, omeprazole/sodium bicarbonate and SmartPill™) is any untoward and unintended response to any of study drugs (nifedipine, omeprazole/sodium bicarbonate and SmartPill™) related to any dose administered.

Unexpected Adverse (Drug) Reaction – is an adverse reaction, the nature or severity of which is not consistent with the applicable product information (e.g., Prescribing Information for an authorized product).

Serious Adverse Event (SAE) / Reaction – a serious adverse event (experience) or reaction is any untoward medical occurrence or effect that at any dose can:

- result in death,
- be life-threatening,
- require hospitalization or prolongation of existing inpatient hospitalization,
- result in persistent or significant disability or incapacity,
- cause a congenital anomaly/birth defect,

- be considered to be other medically important event that may not be immediately life-threatening or result in death or hospitalization, but may jeopardize the participant or may require intervention to prevent one of the above-listed outcomes.

Suspected Unexpected Serious Adverse Reaction (SUSAR) – is all suspected adverse reactions related to PROCARDIA XL, generic nifedipine ER tablets omeprazole/sodium bicarbonate, and SmartPill™, which can occur in the concerned trial, and that are both unexpected and serious.

Unanticipated Problems – The unanticipated problems involving risks to subjects or others to include, in general, any incident, experience, or outcome that meets all of the following criteria:

- unexpected in terms of nature, severity, or frequency given (a) the research procedures that are described in the protocol-related documents, such as the IRB-approved research protocol and informed consent document; and (b) the characteristics of the subject population being studied;
- related or possibly related to participation in the research (“possibly related” means there is a reasonable possibility that the incident, experience, or outcome may have been caused by the procedures involved in the research); and
- suggests that the research places subjects or others at a greater risk of harm (including physical, psychological, economic, or social harm) than was previously known or recognized.

Subjects will be instructed to inform clinic personnel of any untoward medical symptoms and/or events that may arise during the course of the study.

11.2 Characteristics of an Adverse Event

11.2.1 Relationship to Study Drug

The PI/Sub-Investigator will assess the relationship of all adverse reactions to any of study drugs (nifedipine, omeprazole/sodium bicarbonate and SmartPill™), using the following scale:

Probable	A clinical event, including laboratory test abnormality, with a reasonable time sequence to drug administration, unlikely to be attributed to concurrent disease or other drugs or chemicals, and which follows a clinically reasonable response on withdrawal.
Possible	A clinical event, including laboratory test abnormality, with a reasonable time sequence to drug administration, but which

	could also be explained by concurrent disease or other drugs or chemicals. Information on drug withdrawal may be lacking or unclear.
Unlikely	A clinical event, including laboratory test abnormality, with a temporal relationship to drug administration which makes a causal relationship improbable, and which other drugs, chemicals or underlying disease provide plausible explanation.
Unrelated	This category is applicable to AEs which are judged to be clearly and incontrovertibly due to extraneous causes (diseases, environment, etc.) and do not meet the criteria for drug relationship listed for the above-mentioned conditions.

All AEs will be evaluated by the PI/Sub-Investigator, who must approve the subject for subsequent dosing.

Any AEs, whether serious or non-serious, will be monitored throughout the study and followed to resolution, when possible, regardless of whether the subject is still participating in the study.

11.2.2 Expectedness of SAE

The Study PI will be responsible for determining whether an SAE is expected or unexpected as per drug labels. An adverse event will be considered unexpected if the nature, severity, or frequency of the event is not consistent with the risk information previously described for the intervention.

11.2.3 Severity Assessment

The term "severe" describes the intensity (severity) of a specific event; the event itself, however, may be of relatively minor medical significance (such as severe headache). This means it is not the same as "serious", which is based on patient/event outcome or action criteria usually associated with events that pose a threat to a patient's life or functioning³.

The severity of all AEs will be graded by the PI/Sub-Investigator or a medical qualified delegate according to the following definitions:

Mild	Adverse event resulting in discomfort, but not sufficient to cause interference in normal daily activities.
Moderate	Adverse event resulting in discomfort that is sufficient to cause interference in daily activities.
Severe	Adverse event resulting in discomfort causing an inability to carry

E out normal daily activities.

every effort will be made to obtain an adequate evaluation of the severity.

11.3 Adverse Events Reporting

An Adverse Event as defined above generally includes any condition that was:

- 1) Not present prior to administration of study drugs (nifedipine, omeprazole/sodium bicarbonate, SmartPill™) but appeared after initiation of administration of study drug;
- 2) Present prior to administration of study drugs (nifedipine, omeprazole/sodium bicarbonate, SmartPill™) but worsened after administration of study drug; or
- 3) Reported as part of the subject's history, and while not present immediately prior to initiating administration of study drugs (nifedipine, omeprazole/sodium bicarbonate, SmartPill™), reappeared after administration of study drug.

Planned hospital admissions and/or surgical operations/procedures for an illness or disease that existed before the investigational product was given or the participant was enrolled in a clinical trial are not to be considered AEs.

Clinical laboratory data collected during the course of the study, which exceeds or drops below the acceptable limits for the participant population and which, based on baseline values, are considered by the Investigator to be clinically significant, will be reported as an AE. If clinically significant abnormal ECGs and/or laboratory values lead to, or are associated with clinical symptom(s), the diagnosis should be reported as an AE.

If a participant discontinues from the study as a result of an AE, study site personnel must clearly document the circumstances and data leading to the reason for discontinuation.

The investigator/designee is responsible for recording all AEs which have occurred during the study (including clinically important deviations of laboratory values from normal ranges), regardless of their relationship to the study drugs (nifedipine, omeprazole/sodium bicarbonate, SmartPill™). This includes AEs spontaneously reported by the patient, observed by the investigator/designee or elicited by general questioning. All AEs will be determined as Serious or Non-Serious. Treatment of any AEs will be administered under the direction of a physician, either at BPSUSA or at a nearby hospital emergency room.

All symptoms will be recorded by clinic staff and will be reviewed by the PI/Sub-Investigator prior to any subsequent dosing. When appropriate, medical tests and examinations will be performed to document resolution of the event(s).

All reported adverse events will be documented in the Clinical Report.

The Investigator will monitor the subject's condition until recovery to a satisfactory state or stabilization. Thus, follow-up visits may be required even after the administration of the study drugs (nifedipine, omeprazole/sodium bicarbonate, SmartPill™) has been discontinued.

Serious Adverse Events

All serious adverse events (SAEs), whether or not the event is deemed study drug-related, will be reported to the Sponsor by telephone within 24 hours of BPSUSA being aware of SAE, followed by a written report within five business days.

[figure not shown]
Reports of all SAEs must be communicated as soon as possible to the appropriate Institutional Review Board (IRB) or Independent Ethics Committee (IEC) and/or reported in accordance with local laws and regulations.

Adverse events will be coded into the Preferred Term (PT), classified according to the Medical Dictionary for Regulatory Activities (MedDRA) with System Organ Classification (SOC) and reported with severity, duration, onset time and relationship to study drug (nifedipine, omeprazole/sodium bicarbonate, SmartPill™) and action taken.

The Principal Investigator will report to the RIHSC (FDA IRB) through the FDA Sponsor any unanticipated problems involving risk to human subjects or others 45 CFR 46.103(b)(5)(i). Certain adverse events must be reported to the RIHSC within 10 working days of the discovery of the event. The RIHSC defines these adverse events as including, but not limited to the following:

- An adverse event that is not expected, i.e. not listed in the informed consent document or the investigator's brochure;
- An expected adverse event that occurs at a greater frequency or duration than expected;
- Any adverse event that would require modification of the protocol and/or informed consent document

The following Sponsor personnel are to be contacted on the occurrence of a SAE:

11.4 Procedures for Reporting Pregnancy

A positive urine pregnancy test or any hCG level ≥ 5 IU/L for females of child-bearing potential and ≥ 8 IU/L for post-menopausal females will be assessed as clinically significant and will result in the immediate dismissal of the subject from the study, unless deemed otherwise by the Investigator. The elevated hCG will be investigated as a potential pregnancy and will be followed up in the same manner as an AE. A confirmatory hCG blood test will be required for any elevated values. If pregnancy is confirmed, any out of range hCG levels will not be considered an adverse event

Once notified that pregnancy has occurred during the course of the study or within 30 days of study completion, clinic personnel will report the pregnancy within 24 hours of the confirmatory hCG blood test, to the PI/Sub-Investigator, the IRB, and appropriate Sponsor representative. A Pregnancy Notification Form will be completed as per BPSUSA internal Standard Operating Procedures and will be included alongside any pertinent information at the time of pregnancy reporting. The confirmed pregnancy will be followed to birth of the child or elective/spontaneous termination of the pregnancy. Follow up will occur at minimum once every three months (i.e. once per trimester) until the end of the pregnancy (birth, termination, etc.).

Elective termination will not be considered an adverse event; however supporting documentation detailing the outcome of the procedure will be required.

Spontaneous termination of the pregnancy will be considered a Serious Adverse Event and will be followed up accordingly (as per [Section 11.1](#)).

Although elevated hCG and pregnancy will not be considered adverse events, both will be treated as AEs. As such, for safety purposes, the samples collected from any subject who has elevated hCG levels or is confirmed to be pregnant will be analyzed accordingly. Furthermore, the results will not be included in the pharmacokinetic and statistical analysis, but rather will be presented separately.

12.0 BIOANALYTICAL ANALYSIS

12.1 Analytical Procedures

Data management, quality review and reporting of study data pertaining to laboratory analysis of study data will be the responsibility of the bioanalytical facility.

12.1.1 Samples to be assayed

Samples from subjects fulfilling at least one of the following criteria will be analyzed for drug concentration:

1. Subjects who complete at least two study periods.
2. Subjects who have missed samples that have been pre-determined prior to the start of bioanalytical analysis to not significantly impact the overall outcome of the study, as per BPSI PK Scientist and/or Sponsor recommendation.
3. Subjects who do not complete the study due to AE(s).

The samples from subjects who were dismissed due to non-compliance will not be analyzed.

12.1.2 Analyte(s) in Biological Matrix

Plasma samples will be assayed for nifedipine using a validated analytical method according to the principles of Good Laboratory Practice.

13.0 PHARMACOKINETIC AND STATISTICAL ANALYSIS

13.1 Pharmacokinetic Analysis Data Set

The data from the following subjects meeting one of the criteria will be included in the final PK and statistical analysis:

1. Subjects who complete at least two study periods with both test and reference administered alone; or two study periods with the same product administered with and without PPI.
2. Subjects who have missed samples that have been pre-determined prior to the start of bioanalytical analysis to not significantly impact the overall outcome of the study.

Data from subjects who were dismissed or withdrew due to AE(s) will not be included in the PK and statistical analysis. The data for these subjects will be presented separately.

Any decision for excluding data from the final data set will be provided with a detailed explanation and will be properly recorded and dated.

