A question that arises with generic oral ER products is related to pH-dependent dissolution kinetics in comparison with that of their RLD. Depending on the formulation design, poorly water-soluble nifedipine with a pKa in the gastrointestinal (GI) pH range may have pH-dependent solubility. In this case, the in vitro dissolution of matrix-based ER tablets may also be pH-dependent as the drug release is controlled by diffusion driven by a concentration gradient between surface drug concentration and solubility. Bioequivalence (BE) between these

generic products based on a matrix design and their RLDs based on an osmotic pump design is often demonstrated via an *in vivo* bioequivalence pharmacokinetic study using healthy volunteers whose gastric pH is within the physiological norm (e.g. pH 1.2). In this case, ANDA applicants are not required to employ the same release mechanism and formulation design as the osmotic pump RLD. Whether or not the two products are still bioequivalent in subjects with an elevated gastric pH environment as commonly occurred in patients with achlorhydria or population who take concomitant proton pump inhibitors (PPIs) would require additional evaluation.

Food and Drug Administration performed a comprehensive and systematic analysis on generic MR oral drug products in different therapeutic classes based on in-house data on formulations, clinical studies, and post-market surveillance work. The formulations of 15 osmotic pump MR oral drug products and all their approved and pending generic counterparts were identified and analyzed for potential failure modes related to bioequivalence in a risk analysis. Additional modeling work was used to predict the impact of dissolution variations of carbamazepine, metoprolol succinate, venlafaxine HCl (lag time of drug release) [4], and nifedipine (pH-dependent dissolution behavior) MR oral drugs on the resulting PK profiles. These simulation studies helped identify the range of release curve alterations within which the BE of generic products can be maintained and also help suggest potential *in vivo* predictive dissolution conditions. Based on in-house formulation analysis and dissolution testing, a generic version of nifedipine extended-release (ER) tablets using a matrix design has been identified as having pH-dependent dissolution behaviors compared to its reference product (i.e. Procardia XL) in which the drug release is pH-independent.

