Hypothesis 1.2: The hypotheses for testing of the interaction effect between Reference product and the effect of co-administrating PPI/antacid are as follows:

- The null hypothesis (H03): there is statistical significance of the interaction effect if the 90% CI of the ratios of geometric means for AUC_t, AUC_{inf} and C_{max} is less than 80.00%.
- The alternative hypothesis (H13): there is no statistical significance of the interaction effect if the 90% CI of the ratios of geometric means for AUC_t, AUC_{inf} and C_{max} is greater than or equal to 80.00%.
- The null hypothesis (H04): there is statistical significance of the interaction effect if the 90% CI of the ratios of geometric means for AUC_t, AUC_{inf} and C_{max} is greater than 125.00%.
- The alternative hypothesis (H14): there is no statistical significance of the interaction effect if the 90% CI of the ratios of geometric means for AUC_t, AUC_{inf} and C_{max} is less than or equal to 125.00%.

For the relative bioavailability between test and reference products under different conditions (with or without PPI), the calculated 90% confidence interval (CI) for the ratios of geometric means for AUC_t, AUC_{inf} and C_{max} will be used for the following two PK comparisons to assess if the relative bioavailability is or not.

- Test with PPI (Study Arm C)/Reference with PPI (Study Arm D)
- Test without PPI (Study Arm A)/Reference without PPI (Study Arm B) →
Although the generic applicant has already confirmed the bioequivalence between Test and Reference in the absence of PPI, this study will confirm this result.

Hypothesis 2.1: The hypotheses for the assessment of relative bioavailability for Test product with and without PPI are as follows:

- The null hypothesis (H01): there is no comparable bioavailability if the 90% CI of the ratios of geometric means for AUC_t, AUC_{inf} and C_{max} is less than 80.00%.
- The alternative hypothesis (H11): there is comparable bioavailability if the 90% CI of the ratios of geometric means for AUC_t, AUC_{inf} and C_{max} is greater than or equal to 80.00%.
- The null hypothesis (H02): there is no comparable bioavailability if the 90% CI of the ratios of geometric means for AUC_t, AUC_{inf} and C_{max} is greater than 125.00%.

- The alternative hypothesis (H12): there is comparable bioavailability if the 90% CI of the ratios of geometric means for AUC_t, AUC_{inf} and C_{max} is less than or equal to 125.00%.

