5.3 Randomization and Blinding

In this study, the assignment of study arm groups (randomization scheme) will be generated by a computer program designed and run in SAS[®] Version 9.4 [REDACTED]. This is an open-label study and subjects as well as clinic staff will not be blinded to the randomization. The bioanalytical laboratory will not have access to the randomization scheme until the bioanalytical analysis is complete.

Subjects who meet the eligibility criteria will be randomly assigned equally into one of the following four sequence groups:

	Period 1	Period 2	Period 3	Period 4
Sequence 1	A	B	C	D
Sequence 2	B	C	D	A
Sequence 3	C	D	A	B
Sequence 4	D	A	B	C

Each subject is scheduled to receive four periods by the end of the study (See Appendix A).

Study arm A (Test): Nifedipine extended-release tablets [REDACTED]
[REDACTED] 60 mg

Study arm B (Reference): PROCARDIA XL extended-release tablets [REDACTED]
60 mg

Study arm C (PPI/antacid + Test): omeprazole/sodium bicarbonate capsules, 40 mg/1100 mg + Nifedipine extended-release tablets [REDACTED],
[REDACTED], 60 mg.

Study arm D (PPI/antacid + Reference): omeprazole/sodium bicarbonate capsules, 40 mg/1100 mg + PROCARDIA XL extended-release tablets [REDACTED] 60 mg.

The trial will be performed as an open-label study as the pharmacokinetic profile should not be expected to be affected by having the knowledge of reference or generic nifedipine ER tablets was administered. Blinding of the subjects as well as clinic staff is not considered necessary. Only the bioanalytical laboratory staff will not have access to the randomization scheme until the bioanalytical analysis is complete.

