13.3.3 Statistical Analysis

Descriptive statistics (min, max, median, mean, standard deviation and coefficient of variability) of all PK parameters will be provided for nifedipine for all study arm groups.

ANOVA including sequence, subjects nested within sequence, period and study arm will be performed on the ln-transformed data for AUC_t , AUC_{inf} and C_{max} and on the untransformed data for T_{max} , λ and $T_{1/2}$.

T_{max} will be analyzed using an additional non-parametric test (Wilcoxon test).

The 90% CI of the ratios of geometric means for AUC_t , AUC_{inf} and C_{max} will be calculated based on the LSMEANS and ESTIMATE of the ANOVA.

The following PK comparisons will be carried out:

- Test with PPI (Study arm C)/Test without PPI (Study arm A)
- Reference with PPI (Study arm D)/Reference without PPI (Study arm B)
- Test with PPI (Study arm C)/Reference with PPI (Study arm D)
- Test without PPI (Study arm A)/Reference without PPI (Study arm B)

For Pharmacodynamic Data:

The descriptive statistics (min, max, median, mean, standard deviation and coefficient of variability) of the gastric pH and change of gastric pH will be calculated for both test and reference products.

Analysis of Variance (ANOVA) for gastric pH and change of gastric pH from baseline will be carried out.

The following gastric pH comparisons will be carried out:

- Study arm C PPI (Day7) – Study arm A (Day2)

- Study arm D_{PPI (Day7)} – Study arm B_(Day2)
- The comparison of the change between test and reference can be assessed

Additional statistical and alternate tests will be performed if necessary.

Missing data will not be included in the statistical analysis. There are potential two kinds of unbalanced designs for the analysis: (1) unequal number of subjects across groups, (2) missing cells: there are not available data for some subjects. The Type 3 method will be used for the calculation of sums of squares using SAS software. All the fixed effects will be tested using the Type 3 in the ANOVA to detect statistically significant differences ($\alpha=0.05$) if applicable. A mixed effects ANOVA model for gastric pH with fixed factors of sequence, period, and study arm and random effects of subject will be fit. A compound-symmetric or other appropriate covariance structure will be used in the analysis.

The null hypotheses for gastric pH comparisons for different study arms are:

- For the comparison of Study Arm A and Study Arm C

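### Section 13.1 gives a qualifying pair for three of the four planned PK comparisons but not for C/D, so a subject who completes only C and D is assayed and then left out (minor)

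*Combined protocol and SAP*

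**What the plan says.** Sections 4.1 and 13.3.3 both plan four comparisons: C/A, D/B, C/D and A/B. Section 13.3.3 lists the one at issue as "Test with PPI (Study arm C)/Reference with PPI (Study arm D").

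Two rules decide whose data reach those comparisons.

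- **Assay (Section 12.1.1).** The first criterion is "Subjects who complete at least two study periods", whichever arms those are. Subjects who leave because of adverse events are also assayed. Subjects dismissed for non-compliance are not.
- **PK analysis set (Section 13.1).** A subject need meet only one of two criteria. Criterion 1 asks for "two study periods with both test and reference administered alone; or two study periods with the same product administered with and without PPI". Criterion 2 reads, in part, "Subjects who have missed samples that have been pre-determined prior to the start of bioanalytical analysis to not significantly impact the overall outcome of the". A separate sentence adds: "Data from subjects who were dismissed or withdrew due to AE(s) will not be included in the PK and statistical analysis".

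Section 5.3 has subjects "randomly assigned equally into one of the following four sequence groups": ABCD, BCDA, CDAB and DABC. No reason is given for leaving C+D out of criterion 1.

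**The concern.** The inclusion rule appears to have been built from the list of comparisons, with one entry missed. Both products given alone is A+B. The same product with and without PPI is A+C or B+D. Neither phrase can be read to cover both products given with PPI.

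The missing pair serves a key question of the study. Section 3.1 asks "Whether or not the two products are still bioequivalent in subjects with an elevated gastric pH environment", and Section 4.1 notes that the generic applicant has already confirmed bioequivalence without PPI. As written, the rule keeps a partial completer who holds only the A/B pair and drops one who holds only the C/D pair.

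Under Section 7.7 discontinued subjects are not replaced, so a discarded pair cannot be recovered.

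Criterion 2 has a related drafting fault. Because either criterion is enough, tolerable missed samples become a route into the analysis set with no minimum number of periods. A subject with C and D only and a few missed samples could be admitted, while one with complete C and D profiles could not.

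**Working it through.** **1. The plan's own figure.** Section 7.1 states at least 80% power with a minimum of 52 completers, a geometric mean ratio of 1.08, intra-subject variability of about 27% and limits of 80–125%. Section 4.1 specifies two one-sided tests at 0.05.

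- Log-scale SD: s = √ln(1 + 0.27²) = 0.2653.
- Standard error at n = 52: s × √(2/52) = 0.0520, with df = n − 2 = 50.
- Exact TOST power at n = 52 is 87.0% (87.5% with the 4×4 crossover df, 3n − 6 = 150).

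The claim of at least 80% therefore holds.

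**2. Rule against comparisons.** Every two-arm set, checked against criterion 1 and the four planned comparisons:

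| Arms completed | Planned comparison held | Admitted by criterion 1 |
|---|---|---|
| A+B | A/B | Yes |
| A+C | C/A | Yes |
| B+D | D/B | Yes |
| C+D | C/D | **No** |
| A+D | none | No |
| B+C | none | No |

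Every three-arm set, and the full set, contains A+B, A+C or B+D and is admitted. C+D alone is the only excluded set that holds a planned pair.

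**3. Who this is.** If subjects leave and do not return, the sets after Period 2 are AB (Sequence 1), BC (Sequence 2), CD (Sequence 3) and DA (Sequence 4). Seven dropout or completion patterns contain both C and D: ABCD, BCD, BCDA, CD, CDA, CDAB and DABC. Criterion 1 excludes only CD, which is Sequence 3 stopping after Period 2. A subject who skipped both A and B without dropping out would also be caught, but that would be rare.

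**4. How many.** Allowed losses are 65 − 52 = 13 to 66 − 52 = 14. The documents do not say how losses fall, so this is assumed.

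- Even spread over 4 sequences and 3 stopping points: 13/12 = 1.1 to 14/12 = 1.2 subjects.
- All losses after Period 2, even over sequences: 13/4 = 3.25 to 14/4 = 3.5 subjects.

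Both counts are before removing adverse-event withdrawals and non-compliance dismissals, who are excluded for other reasons.

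**5. What each is worth.** Take the Section 13.3.3 model (subject within sequence, period, arm) with 52 completers, 13 per sequence, and add one Sequence 3 subject with C and D only. Let σ² be the within-subject variance.

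| Comparison | Variance, 52 completers | With the added subject | Reduction |
|---|---|---|---|
| C/D | 2σ²/52 = 0.03846σ² | 0.03775σ² | 1.85% |
| C/A | 0.03846σ² | 0.03828σ² | 0.46% |
| D/B | 0.03846σ² | 0.03828σ² | 0.46% |
| A/B | 0.03846σ² | 0.03846σ² | none |

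In power terms one subject near n = 52 is worth about 0.6 points: 86.4% at 51 and 87.0% at 52. Power is still 84.5% at 48.

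**The case against.** The strongest reply is that the gap hardly matters. All 52 required completers contribute both C and D, the subjects at stake number one or a few, and power does not approach 80%. That is correct, and it sets the severity.

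Four stronger readings are tempting, and the documents do not support them.

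- **That anyone with complete C and D profiles is excluded.** A subject who also completes A enters through A+C, and one who also completes B enters through B+D. Nor does it matter whether A and B later prove unusable, because criterion 1 turns on completing periods.
- **That only C/D loses information.** Step 5 shows small losses for C/A and D/B too.
- **That the rule alone makes retention depend on sequence.** After Period 2, Sequences 2 and 4 hold B+C and D+A, which are not planned pairs. They stay out under any rule based on planned pairs, including the one proposed here.
- **That C/D is the designated primary comparison.** No comparison carries that label, the title describes a drug-drug interaction study, and Section 4.1 lists C/A and D/B first. The rationale supports calling C/D a key question and no more.

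On criterion 2, entry is not automatic: missed samples must be judged, before bioanalysis, not to affect the outcome. That limits the practical risk but does not repair the either/or wording.

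Section 13.3 allows analyses to be altered with justification, so the pair could be added later. But clinic staff are not blinded to treatment (Section 5.3), and inclusion is better settled by rule than case by case.

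**Conclusion.** The omission is real. Criterion 1 of Section 13.1 has no entry for one of the four planned comparisons, and no other section supplies it. A subject who completes C and D only, and leaves for a reason other than an adverse event or non-compliance, is assayed under Section 12.1.1 and then excluded despite holding a complete planned pair.

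The point is minor. The estimate of about 1 subject rests on an even spread of the allowed losses, and about 3.5 on all of them falling after Period 2; the documents support neither pattern in particular. A reader might infer that the C/D comparison is underpowered or biased by the rule. The figures do not show that: power remains above the stated 80% on the protocol's own assumptions, and nothing here establishes a direction of bias. The case for acting is that usable, already assayed data would be discarded for no stated reason.

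**What to change.** Before bioanalysis starts, amend Section 13.1 in two places.

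1. Reword criterion 1 to admit subjects who complete at least one planned pair: A+B, C+D, A+C or B+D.
2. Make criterion 2 a condition on individual concentration profiles that applies in addition to criterion 1, so that missed samples are not a separate route to inclusion.

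The separate exclusions for adverse-event withdrawals and non-compliance are not touched by this change. The cost is a sentence or two of protocol wording. No further samples or assays are needed, because Section 12.1.1 already covers these subjects.
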